### **8.2.4 Sensitivity Analysis Including Imputation of Missing Data**

Multiple imputation is commonly used in the analysis of MNAR data. For all randomized subjects who withdraw early, imputation of missing data will be applied to projected visits up to their planned end of the trial (12 months post-randomization). The subjects' reasons for discontinuation will be captured and categorized to help determine the missing data pattern. Imputation will be based on the data used in the MMRM model specified in [Section 8.2.2](#). In order to perform the analysis of random coefficient regression model specified for the key secondary endpoint, simulated value of a missing data will be assigned a value for the time variable used in regression which is equal to the time of its previous visit plus 30.5 days. For placebo subjects, and in the absence of evidence suggesting biased missing data pattern, the imputation will follow the placebo trend.

[REDACTED]

[REDACTED]. The imputation of these tolvaptan withdrew subjects is based on the following:

These imputed data will be added to the data described in [Section 8.2.1](#) and [Section 8.2.3](#) for two sets of sensitivity analyses. In each set of sensitivity analysis, reason of discontinuation will be classified in the following order as:

- 1) Progression of renal disease
- 2) Lack of efficacy
- 3) Other Adverse Event
- 4) Aquaretic AE (MedDRA preferred terms of THIRST, POLYURIA, NOCTURIA, POLLAKIURIA, POLYDIPSIA)
- 5) Trial too burdensome
- 6) Commercial tolvaptan for ADPKD available

This lists reasons for missing data due to discontinuation of trial participation in a decreasing order of their likelihood to produce data MNAR. Specifically, MNAR in the following patterns of dropout reasons will be investigated:

1. Progression of renal disease and Lack of efficacy (LOE) in tolvaptan treatment group as MNAR
2. Progression of renal disease, LOE, and other adverse events (AE) in tolvaptan treatment group as MNAR

[REDACTED]

Therefore, the following delta adjustment imputation method will be applied:

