7.4.2.4 Sensitivity Analysis Including Imputation of Missing Data

Multiple imputation is commonly used in the analysis of MNAR data. For all randomized subjects who withdraw consent for further testing or who are lost to follow up, imputation of missing data will be applied to projected visits up to their planned end of the trial (12 months post-randomization). The subjects' reasons for discontinuation will be captured and categorized to help determine the missing data pattern (see [Section 3.8.3.4](#)). Imputation will be based on the MMRM model specified in [Section 7.4.2.2](#). For placebo subjects, and in the absence of evidence suggesting biased missing data pattern, the imputation will follow the placebo trend.

Post-withdrawal data from Trial 156-04-251 and Trial 156-08-271 interim analyses show that tolvaptan's eGFR benefits accumulate and are sustained after treatment discontinuation; therefore, imputation for subjects randomized to tolvaptan should reasonably begin at the value of their last eGFR. If a subject has the post-treatment follow-up in the two-week interval, imputation will be based on this post-treatment observation; if a subject does not have the post-treatment follow-up observation, imputation will be based on the last on-treatment observation and flagged with the tolvaptan acute hemodynamic effect mentioned in [Section 7.4.2.1](#).

Trial [REDACTED] data also support true disease modification and preservation of functioning kidney parenchyma through reduction of cyst growth. Thus, discontinuation of tolvaptan would not result in an immediate return to the placebo trend. Therefore, eGFR decline in subjects discontinuing tolvaptan will reasonably fall somewhere between the tolvaptan trend and placebo trend. This supports a series of analyses for imputation of missing data for tolvaptan subjects, which will begin using the tolvaptan trend, and move stepwise toward the placebo trend. Further details will be provided in the SAP.

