**Delta Adjustment Imputation Method**

This MNAR sensitivity analysis is to investigate the departure from MAR assumption by progressively decreasing the treatment differences over the missing visits in those treated subjects who fell into an assumed MNAR pattern. This progressive decrease of treatment slope difference is carried out by subtracting k times the expected treatment difference (in the absent of the hemodynamic effect) from the imputed missing data after dropout using tolvaptan slope in those treated subjects who fell into an assumed MNAR pattern, with k starts from 0%, 10%, 20%, ..., and up to 100% or higher, until conclusion from the

analysis of the key secondary endpoint is overturned (it is called tipping point analysis), or it becomes clinically meaningless to go even higher. The expected treatment difference between tolvaptan and placebo at a visit may be derived from the treatment difference in slope, multiplied by the visit month number and divided by 12. Note that when 0% is used, the MI procedure would produce an analysis which is essentially MAR. When 100% is used, the MI procedure would produce an analysis which is essentially something called “copy placebo”. Specifically the MI procedure follows these steps:

- Using Monte Carlo Markov Chain (MCMC) methodology from PROC MI by treatment group to impute the intermittent missing data to a monotone missing pattern;
- Using a standard MAR-based multiple imputation approach from PROC MI to impute data from monotone missing data;
- For subjects in the treated groups who fall into a MNAR pattern specified above, a delta which equal to k times their treatment differences mentioned above will be subtracted for their imputed values after the dropout time, with k described in the above paragraph;
- Using the random coefficient regression model specified in the previous section to analyzed the completed data along with the imputed data;
- Obtaining the overall results using PROC MIANALYZE.

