will be mapped to visit Month 12. If an unscheduled visit or an end of treatment visit is more than 2 days post last dose, it will not be mapped to these double-blind nominal visits, but will be considered for the post-treatment follow-up visits, if it falls within 7 to 40 days from the last dose of IMP.

(12) The following reasons are collected in the CRF for subjects who discontinue IMP:

1. Discontinued based on subject decision:
  - 1.1. IMP not tolerable (AE which is annoying or uncomfortable but not serious or hazardous)
  - 1.2. Reason other than tolerability
    - 1.2.1. Pregnancy
    - 1.2.2. Trial too burdensome
    - 1.2.3. Other reason
  - 1.3. Taking marketed product for tolvaptan
2. Discontinued based on physician decision
  - 2.1. Potential IMP-related safety concern or serious AR placing subject at undue hazard
  - 2.2. Progression of disease leading to dialysis, transplantation or eGFR decline
  - 2.3. Hepatic AE
3. Other
  - 3.1. Subject death
  - 3.2. Subject lost to follow-up

In [Section 8.2.4](#) for sensitivity analysis including imputation of missing data, six reasons of discontinuation of IMP were listed in the order of their likelihood to be MNAR. The mapping of the reasons of discontinuation of IMP to the reasons used in the sensitivity analysis is provided below:

- Progression of renal disease or Lack of efficacy: Item 2.2
- Other AE: Items of 1.2.3, 2.1, 2.3, 3.1 and 3.2
- Aquaretic AE: Item 1.1
- Trial too burdensome: Items of 1.2.1 and 1.2.2
- Commercial tolvaptan for ADPKD available: Item 1.3

The reason to map Items of 1.2.3 (Other reasons under Reason other than tolerability) and 3.2 (Subject lost to follow-up) to other AE is for conservativeness to consider them as a reason to be more likely MNAR.

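### The tipping-point imputation in SAP 8.2.4 leaves tolvaptan dropouts for intolerance, pregnancy, burden and commercial drug at the tolvaptan trend at every k, a narrower scope than Protocol 7.4.2.4

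*SAP*

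**What the plan says.** Protocol 7.4.2.4 argues that, after tolvaptan is stopped, eGFR decline should lie between the tolvaptan and placebo trends. It therefore plans a series of analyses with "imputation of missing data for tolvaptan subjects, which will begin using the tolvaptan trend, and move stepwise toward the placebo trend". It names no reason for stopping as exempt. It does say that reasons will be categorized to help identify the missing-data pattern, and it leaves further detail to the SAP. The subjects imputed are given as "For all randomized subjects who withdraw consent for further testing or who are lost to follow up".

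SAP 8.2.4 widens the imputed group: "For all randomized subjects who withdraw early, imputation of missing data will be applied to projected visits". It lists six reasons in falling order of likelihood of being MNAR and then defines two patterns. The first is "Progression of renal disease and Lack of efficacy (LOE) in tolvaptan treatment group as MNAR" and the second is "Progression of renal disease, LOE, and other adverse events (AE) in tolvaptan treatment group as MNAR". Under the Delta Adjustment Imputation Method, k times the expected treatment difference is subtracted "from the imputed missing data after dropout using tolvaptan slope in those treated subjects who fell into an assumed MNAR pattern". The value of k rises in 10% steps to 100% or beyond, until the conclusion is overturned or a further increase would have no clinical meaning.

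SAP 8.3(12) maps CRF reasons to these categories. Other AE takes in other reason, IMP-related safety concern, hepatic AE, death and loss to follow-up. Item 1.1 (IMP not tolerable) goes to Aquaretic AE, item 1.3 (marketed tolvaptan) has its own category, and the remaining line reads "Trial too burdensome: Items of 1.2.1 and 1.2.2".

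**The concern.** The protocol's reason for moving imputed values toward placebo is loss of drug exposure. That applies to a subject who stops because of polyuria as much as to one who stops because of progression. The SAP ranks all six reasons for MNAR risk but never varies the assumption for the last three. Protocol 1.4 names aquaretic reactions as those most likely to limit continued therapy, and they are drug effects, so such dropout can be expected to differ between arms.

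The coding adds a second gap. Item 1.1 covers any AE that is bothersome but neither serious nor hazardous. SAP 8.2.4 defines Aquaretic AE by five preferred terms (thirst, polyuria, nocturia, pollakiuria, polydipsia). A subject who leaves with, say, a non-serious headache would be Other AE by the 8.2.4 definition and would be shifted. Under the 8.3(12) mapping that subject is Aquaretic AE and is not.

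At stake is how a tipping-point result is read. SAP 8.2.4 describes k = 100% as in essence a copy-placebo analysis. That is true only of the shifted subset, so a reader could overestimate the stress applied.

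**Working it through.** **1. Who is shifted.** Reading SAP 8.2.4 with 8.3(12), tolvaptan arm only:

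| CRF item | Category in 8.3(12) | Pattern 1 | Pattern 2 |
|---|---|---|---|
| 2.2 progression | Progression or lack of efficacy | shifted | shifted |
| 1.2.3 other reason, 2.1 safety concern, 2.3 hepatic AE, 3.1 death, 3.2 lost to follow-up | Other AE | no | shifted |
| 1.1 IMP not tolerable | Aquaretic AE | no | no |
| 1.2.1 pregnancy, 1.2.2 burdensome | Trial too burdensome | no | no |
| 1.3 marketed tolvaptan | Commercial tolvaptan | no | no |

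Tables CT-5.2.4.1 to CT-5.2.5.2 (SAP Appendix 3) and Figures 4.1 to 4.4 (Appendix 4) list these two patterns for two data sets and no third. Text around the pattern list is redacted, so a rationale may exist that cannot be seen.

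**2. The plan's own figures.** The key secondary calculation (SAP 4.1) takes a placebo decline of 4.5 per year, a 25% reduction, two-sided alpha 0.05, 1:1 allocation and 734 subjects for 90% power. The variances are redacted, so 734 cannot be rebuilt. It can be inverted with the two-means formula:

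- Effect D = 0.25 × 4.5 = 1.125.
- Implied SD = 1.125 / [(1.960 + 1.282) × √(2/367)] = 4.70.
- With N = 1300 less 10% dropout = 1170, SE = 4.70 × √(4/1170) = 0.275 and z = 1.125/0.275 = 4.09.
- Power is 98.3% at 1170 and 99.1% at 1300, in line with the stated figure of more than 90%.

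The same formula with the primary inputs (effect 1.07, variance 28.05 + 14.2/draws, division by 0.90) gives 1725, 1436, 1338 and 1292. The plan's table has 1722, 1434, 1336 and 1288.

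**3. Effect of the delta.** Let f be the share of the tolvaptan arm shifted. Let c be the part of the slope difference removed from a dropout's completed-data slope at k = 100%. Then:

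- difference at k = D × (1 − f·k·c)
- tipping k = (1 − 1.96/z) / (f·c), where z is the MAR result

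A least-squares fit on months 1 to 12 gives c between 1.00 and 1.32 for dropout up to month 9 and 0.46 at month 11. I use c = 1. Extra imputation variance and the hemodynamic flag are ignored. The shares f are assumed.

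| f | z at k = 100% (MAR z = 4.09) | tipping k | z at k = 100% (MAR z = 2.1) | tipping k |
|---|---|---|---|---|
| 20% | 3.27 | 260% | 1.68 | 33% |
| 10% | 3.68 | 521% | 1.89 | 67% |
| 5% | 3.89 | 1042% | 2.00 | 133% |
| 2% | 4.01 | 2604% | 2.06 | 333% |

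At the planned effect, tipping requires a loss of 1 − 1.96/4.09 = 52% of the slope difference. At z = 2.1 it requires 1 − 1.96/2.1 = 6.7%. With c = 1.3 the 10% and 5% figures at z = 2.1 become 6.7/(0.10 × 1.3) = 51% and 6.7/(0.05 × 1.3) = 103%.

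**4. Where scope changes the verdict.** At k = 100% and c = 1, shifting 10% loses significance when the MAR z is below 1.96/0.90 = 2.18. Shifting 5% does so below 1.96/0.95 = 2.06. Between these values, and only there, the choice between 10% and 5% decides the result at k = 100%.

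**The case against.** A reader might infer that the restriction is why the analysis could hardly tip. The documents do not support that. The value of k has no numerical cap. Other AE is broad, and the SAP says that other reason and loss to follow-up were placed there to be conservative. At planning inputs, shifting every dropout at 10% also fails to tip at k = 100%; high planned power and low assumed dropout explain this, not the reason codes.

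A reader might also say that the SAP breaks a protocol commitment. That goes too far, because the protocol foresees categories by reason and defers detail to the SAP. In two respects the SAP is wider: it imputes for all early withdrawals and lets k pass the placebo trend.

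Other points carry weight:

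- The estimand (Protocol 7.4, SAP 8.1) supposes full tolerance and adherence, which fits keeping tolerability dropouts at MAR.
- The second data set adds imputations to the SAP 8.2.3 data, where IMP discontinuers who stay in follow-up contribute observed off-treatment values.
- Protocol 1.4 says aquaretic reactions occur early, and titration and run-in are meant to remove those subjects before randomization. It does not predict that they will dominate later dropout.
- Subjects who leave for marketed tolvaptan may still be on the drug, so a placebo trend may not suit them.

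These points limit the size of the concern. None of them exempts intolerance or burden dropouts from a test of MAR, which SAP 8.1 says the sensitivity analyses will address. The alternative stop for k has no numerical definition, and a small shifted subset pushes the tipping k far beyond the placebo trend, where that stop could be invoked.

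**Conclusion.** The point holds as a gap in scope and a coding inconsistency in one sensitivity analysis of the key secondary endpoint. Items 1.1, 1.2.1, 1.2.2 and 1.3 are never shifted, the protocol states no such limit, and non-aquaretic intolerance escapes through the mapping of item 1.1.

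The tipping k is inversely proportional to the share shifted, so covering half the dropouts doubles it. The practical effect is nil at k = 100% under the planned effect and can decide the conclusion only when the MAR result is close to the boundary. How much narrower the planned patterns are than an all-dropout version cannot be stated, because dropout by reason is not in the documents. Any multiple quoted for it would only restate the assumed shares. The arithmetic also rests on an SD inverted from 734 and on c near 1. This is a cheap improvement rather than a fault that threatens the trial's conclusion.

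**What to change.** In SAP 8.2.4, on the same k grid and for both data sets:

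- Add a third pattern that shifts the reasons in pattern 2 plus item 1.1.
- Add a fourth pattern that shifts all tolvaptan subjects with imputed data, shown with and without item 1.3.
- Classify item 1.1 subjects by AE preferred term, following the 8.2.4 definition of Aquaretic AE, and align 8.3(12) with it.
- Report the number of subjects shifted and the tipping k for every pattern.
- Base any statement on robustness on the broadest pattern as well as the two already planned.

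The matching tables and figures go into Appendices 3 and 4. The cost is some SAP wording, a few more runs of the same code, and possibly a less favourable sensitivity result.

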**Delta Adjustment Imputation Method**

This MNAR sensitivity analysis is to investigate the departure from MAR assumption by progressively decreasing the treatment differences over the missing visits in those treated subjects who fell into an assumed MNAR pattern. This progressive decrease of treatment slope difference is carried out by subtracting k times the expected treatment difference (in the absent of the hemodynamic effect) from the imputed missing data after dropout using tolvaptan slope in those treated subjects who fell into an assumed MNAR pattern, with k starts from 0%, 10%, 20%, ..., and up to 100% or higher, until conclusion from the

analysis of the key secondary endpoint is overturned (it is called tipping point analysis), or it becomes clinically meaningless to go even higher. The expected treatment difference between tolvaptan and placebo at a visit may be derived from the treatment difference in slope, multiplied by the visit month number and divided by 12. Note that when 0% is used, the MI procedure would produce an analysis which is essentially MAR. When 100% is used, the MI procedure would produce an analysis which is essentially something called “copy placebo”. Specifically the MI procedure follows these steps:

- Using Monte Carlo Markov Chain (MCMC) methodology from PROC MI by treatment group to impute the intermittent missing data to a monotone missing pattern;
- Using a standard MAR-based multiple imputation approach from PROC MI to impute data from monotone missing data;
- For subjects in the treated groups who fall into a MNAR pattern specified above, a delta which equal to k times their treatment differences mentioned above will be subtracted for their imputed values after the dropout time, with k described in the above paragraph;
- Using the random coefficient regression model specified in the previous section to analyzed the completed data along with the imputed data;
- Obtaining the overall results using PROC MIANALYZE.

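### The MNAR delta in SAP 8.2.4 counts months from randomization, so k = 100% is a jump to the placebo mean and not the move from the last eGFR that Protocol 7.4.2.4 describes

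*SAP*

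**What the plan says.** SAP 8.2.4 (Delta Adjustment Imputation Method) first imputes under MAR and then penalizes tolvaptan subjects whose dropout reason falls in an MNAR pattern. The starting point is the "imputed missing data after dropout using tolvaptan slope". From this, k times the expected treatment difference is removed, and the delta "will be subtracted for their imputed values after the dropout time". The difference at a visit may be "derived from the treatment difference in slope, multiplied by the visit month number and divided by 12". The stated aim is "progressively decreasing the treatment differences over the missing visits", with k raised from 0% in steps of 10% to 100% or beyond until the key secondary conclusion is overturned.

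Projected visits run to "12 months post-randomization", and SAP 8.3 item 6 uses a Month 1 to 12 axis with mean 6.5, so the month number counts from randomization. For the upper reference point the SAP says: "When 100% is used, the MI procedure would produce an analysis which is essentially something called" copy placebo. The term is not defined.

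Protocol 7.4.2.4 states that "imputation for subjects randomized to tolvaptan should reasonably begin at the value of their last eGFR" and that "discontinuation of tolvaptan would not result in an immediate return to the placebo trend". It expects decline after discontinuation to lie between the two trends, asks for a series moving stepwise from the tolvaptan trend to the placebo trend, and leaves the detail to the SAP.

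**The concern.** A tipping-point analysis is summarized by one number, k, and a reader can use that number only if the scale is clear. Under the SAP rule the amount removed at a missed visit depends on time since randomization, including the months the subject was observed on treatment. Benefit already accrued when the subject left is taken away at once. The protocol's premise is that this benefit is kept and only the later course is in doubt.

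At stake is how a tipping k below or near 100% would be read. A reader told that 100% means placebo-like might conclude that the result fails before dropouts decline at the placebo rate, when it would survive that scenario.

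**Working it through.** **Inputs.** Placebo decline 4.5 per year and a 25% reduction on tolvaptan (Protocol 7.1.1, SAP 4.1) give a slope difference D = 4.5 × 0.25 = 1.125 and a tolvaptan slope of -3.375. Visits are Months 1 to 12. Let d be the month of the last on-treatment visit and m a later, missed visit.

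**Month axis.** The SAP gives no figure for the k = 100% case, only a label. Its 6/143 scaling factor (8.3 item 6) can be reproduced. The contrast coefficients are redacted, but with odd integers from -11 to 11 on Months 1 to 12 the sum of coefficient × month is 286, and 12/286 = 6/143. This supports the Month 1 to 12 axis.

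**Mean at k = 100%.** Tolvaptan mean minus delta is -3.375 × m/12 - 1.125 × m/12 = -4.5 × m/12, the placebo mean, whatever d is. For d = 6 and m = 7:
- SAP rule: -1.969 - 0.656 = -2.625.
- Placebo slope from the last value: -3.375 × 6/12 - 4.5 × 1/12 = -2.0625.
- The gap, 0.5625, is the whole benefit accrued by Month 6 (1.125 × 6/12).

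**Decomposition.** k × D × m/12 = k × D × d/12 + k × D × (m - d)/12. The first term is a step at the first missed visit. It vanishes only at k = 0, so no k above zero gives a course that starts at the last value.

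**Delta at k = 100%**

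| Last visit d | First missed visit, SAP | First missed visit, from dropout | Month 12, SAP | Month 12, from dropout | Ratio at Month 12 |
|---|---|---|---|---|---|
| 3 | 0.375 | 0.094 | 1.125 | 0.844 | 1.33 |
| 6 | 0.656 | 0.094 | 1.125 | 0.563 | 2.0 |
| 9 | 0.938 | 0.094 | 1.125 | 0.281 | 4.0 |

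**Average factor.** Assume dropout spread evenly over d = 1 to 11. At visit m, summing over d = 1 to m - 1, the SAP rule contributes m(m - 1) units and the since-dropout rule m(m - 1)/2. The ratio is exactly 2.

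**Slope removed at k = 100%.** This is a single-subject least-squares slope, with zero delta at observed points.
- Days -36, -8, -1 and Months 1 to 12: 1.16 against 0.47 for d = 6; average over d = 1 to 11, 0.99 against 0.49.
- Months 1 to 12 only: average 1.23 against 0.61.
- First set plus follow-up at Days 8, 14 and 21 after dropout (days assumed): average 0.91 against 0.49.

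**Effect on tipping k.** Assume 10% of the tolvaptan arm in the MNAR pattern, an estimated difference of 1.125 and a standard error unaffected by k. The room before significance is lost is 1.125 × (1 - 1.96/z).
- z = 2.1: room 0.075. Tipping k = 0.075/(0.10 × 0.986) = 0.76 (SAP) against 0.075/(0.10 × 0.493) = 1.52 (from dropout). With Months 1 to 12 only, 0.61 against 1.22.
- z = 3.24 (1.96 + 1.28, the 90% power case): room 0.444. Tipping k is about 4.5 against 9.0, or 3.6 against 7.2 with Months 1 to 12 only.

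**The case against.** The rule can be defended as a deliberately severe stress test. In plain words, putting missed visits on the placebo mean is placebo-like, and it meets the SAP's stated aim of shrinking the difference at those visits to zero. The grid of k values is itself a stepwise series. The formula is permissive, and text just before the method is redacted, so a rationale may exist that cannot be seen. These points stand as reasons to keep the current version. They do not make it the scenario in Protocol 7.4.2.4, because every k above zero carries the step.

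The proposed addition is not a perfect match either: at k = 100% the slope returns to the placebo rate immediately, though from the last value, and only the intermediate k values lie between the trends.

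Three stronger readings are tempting and not supported:
- That the SAP is plainly wrong to say copy placebo. The term is undefined and hedged, so it is a mislabel only by the usual names of reference-based methods. Under those names the current rule is jump-to-reference in mean, and the since-dropout rule is copy-increments, so neither earns the label.
- That k = 100% typically makes a dropout's fitted slope steeper than placebo. On Months 1 to 12 alone, dropout after Month 6 removes 1.48, more than 1.125. The model in SAP 8.2.1 also uses the run-in points; with those it is 1.16, or 1.08 with follow-up as well, and the averages of 0.99 and 0.91 fall below 1.125.
- That the tipping point will be misread. If k tips well above 100% on the SAP scale, the milder scenario is survived all the more.

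**Conclusion.** The point holds. The SAP's delta is a jump to placebo in mean at k = 100%, and it does not implement the protocol's premise that imputation starts at the last eGFR. At k = 100% it removes about twice as much slope, on average, as a delta counted from dropout.

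The consequences are limited. The discrepancy works against tolvaptan, so it cannot create a false impression of robustness. It touches only the MNAR sensitivity analyses of the key secondary endpoint, not the primary test or the type I error. With 10% of the arm affected, the two rules differ at k = 100% by 0.10 × (0.99 - 0.49) = 0.05 per year, about 4% of 1.125. It matters for a borderline key secondary result and not for one near the planned power.

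The step at the first missed visit is exact algebra. The averages rest on planning slopes, even dropout over Months 1 to 11, and least squares as an approximation to the mixed model with its hemodynamic flag. The tipping values also rest on the assumed 10% share and z.

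**What to change.** In SAP 8.2.4:
- Add a second delta, k × slope difference × (visit month - month of last on-treatment visit)/12, labelled 'placebo slope from the last value'.
- Keep the current delta, labelled 'jump to placebo', and state that its month number counts from randomization.
- Replace the copy placebo sentence with these two labels.
- Report tipping k separately on each scale.

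The cost is a few lines of text and one extra multiple-imputation run. The added version is less severe than the current one, so both must be shown to avoid any appearance of softening the test.
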